- Utilising the same 'dosage' and type of interventions (groups with similar structure, delivery times and requirements for practice) utilising MfH-MBPM and MfS (Burch and Penman 2013, Hennessy 2017)
- Using appropriate psychometric and qualitative analysis and targetting of explicit process-change.
- Reporting adverse side effects
- Measures in line with IMMPACT recommendations for research on chronic pain (Dworking *et al.*, 2005).

iii. **Study design, to include recruitment and sampling strategy, inclusion/exclusion criteria, sample size and justification:**

In order to address the research questions, the current study will be divided in and presented as separate quantitative and qualitative components:

Quantitative study:

Design and Method

DESIGN

A waiting-list controlled, randomised, pilot trial of mindfulness based group treatment comparing two active standardised interventions (mindfulness for stress vs. mindfulness for pain/health)

SETTING AND STUDY POPULATION

An opportunity sample via general practice, waiting-room advert and GP supported recruitment in Jersey, serving a population of 106,000, will be invited to take part in the study.

RECRUITMENT

All general practices in Jersey will be invited to take part in this study. They will be recruited through the Jersey Primary Care Body and Social Media Advertising.

CASE IDENTIFICATION

Over a six months period.

Once potential participants have consented, searches will be run on GP electronic health records to identify suitability. Demographic data including gender, age, ethnicity and employment status, pain diagnoses, current medication and dosage, co-morbidities and mental health diagnoses will be extracted via GP referral to the study, including that the patients meet inclusion criteria and do not meet any of the exclusions.

INCLUSION AND EXCLUSION CRITERIA (PATIENTS)

Inclusion criteria:

1. Pain > 3 months
2. Ability to communicate and literacy in English
3. Age 18 years or older
4. No current outstanding medical tests or procedures for conditions expected by the GP to interfere with participation in treatment.
5. Has not previously received non-medical treatment at a specialist pain centre, or

attended a multidisciplinary pain management programme.

6. Ability to utilise online video conferencing technology (i.e. ownership of a compatible device & necessary technical competence)

Exclusion criteria:

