4) *Cognitive fusion:* the Cognitive Fusion Questionnaire (Gillander *et. al*, 2014)

5) *Values:* The Chronic Pain Values Inventory (McCracken and Yang 2006)

6) *Committed Action:* The 8-item Committed Action Questionnaire (McCracken, Chilcot et al. 2015)

Outcome measures:

Pain Intensity and interference on quality of life : the Brief Pain Inventory – Short Form (Tan, Jensen et al. 2004), numeric rating scale (NRS) on intensity (scale 0-10) including, worst, least

average (in the past week) and right now. BPI interference scale for impact on quality of life.

Emotional Functioning

a. *Pain related distress:* The Pain Catastrophizing Scale (Sullivan, Bishop et al. 1995)

b. *Depression:* The Beck Depression Inventory – Fast Screen (Poole, Bramwell et al. 2009)

Global Impression of Functioning: the Patient's Global Impression of Change (Guy 1976) will allow to consider perceived improvement and deterioration.

Qualitative:

DATA ANALYSIS

Transcribed data will be managed with NVivo software. All transcripts will be read and reread to ensure familiarity with the data. We will use thematic analysis (Braun and Clarke 2006) to identify recurring themes across the data and examine relationships between themes. The thematic analysis will be undertaken by two researchers independently coding for emerging themes and then comparing codes and themes.

TOPIC GUIDE

Do you have any previous experience in taking part in clinical trials or medical research?

I'm really interested in finding out what were your initial expectations and feelings about the mindfulness course?

What do you feel you have gained from attending the course?

What (if any) changes have you noticed in your health/quality of life? [probe for anything getting better or worse: health, emotional, physical, practical]

How do you feel the course has contributed to how you manage chronic pain?

This study has involved you doing some reading, meditation and practices in everyday life ('habit releasers'). Would you give me a sense as to whether you have managed to engage in these practices? [Ask about how long typically they have practiced daily formal meditation; are they still practising?; What has stuck and what hasn't?]

Is there anything else you would like to say about your experience of the course?

How do you feel the teacher contributed to your experience of the course?

What contribution do you feel the group has made to what you have learnt?

Since attending the course:

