Also see Risk Assessment in Appendix. In addition, the lead researcher will remain as contactable throughout the project and will provide advice, risk assessment and signposting throughout the project. At the outset of each group and as part of group agreement and rules, all participants will be made aware of the need to speak to the facilitators should they experience any significant adverse physical or emotional difficulties requiring further medical or psychological attention.

i. Are there any potential risks or adverse effects to participants?

As well as any physical risks or adverse effects, you should consider the potential for discomfort, distress, inconvenience or change in lifestyle for the participants, and explain how these will be managed.

See Risk Assessment

ii. Are there any particular requirements or abstentions that will be imposed on participants? (Eg. multiple attendance sessions; abstention from alcohol, tobacco, etc.).

Participants will be required to attend all 8 sessions of the mindfulness course and will be classed as completers with a minimum of 6 sessions.

Participants will be required to abstain from alcohol, illegal or otherwise mentally impairing substances.

Participants will be required to keep a log of their personal-time practice, read the appropriate course manual/book and complete their home mindfulness practice.

iii. Are there any potential benefits to participants, or to the wider society?

Given the evidence presented earlier and the broader evidence of mindfulness, the current costs of attending mindfulness courses, participants will be able to complete a full and Breathworks accredited Stress or Pain Course, which also provides the basis for future mindfulness teacher training in line with current UK standards. These courses would usually retail in the region of £190-£350 per head.

As the courses will be offered to a community sample, this will not prevent patients with chronic pain from accessing the current provision at the local pain management centre. In actual fact, it will give opportunity to more people to access both stress and pain courses.

Above and beyond the benefits to understanding research, they will contribute to furthering understanding, improving provision of pain specialist services and to pain professionals competency standards.

The benefits of mindfulness go beyond pain and include those to the workplace, team working, productivity, stress and performance and general wellbeing.

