[name] has agreed to fund materials (books that are used as course manuals, stationery for psychometric and interview material, floor mats, refreshments and utilisation of group room within the premises outside of the times used by the clinics regular courses). The anticipated cost of books is in the region of £1000, mats & stationery £200 & refreshments £40 Total: £1240

Stationary costs will be will be mitigated with the use of online survey tools where possible (surveymonkey).

4. What arrangements are in place for monitoring the conduct of the research, and dealing with any issues, complaints or adverse effects which may arise from the research?

[Note that, in the first instance, complaints should be addressed to the Academic Research Supervisor or the sponsoring Head of Department]

The lead researcher will be the point of contact for any adverse effects (distressing thoughts or emotions) arising from the intervention. However, to mitigate this, no participant with current diagnosis of PTSD or active psychiatric condition requiring treatment, or drugs and alcohol dependence will be accepted on the trial (part of the exclusion criteria) as part of the recruitment process.

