Appendix 7: Risk Assessment Form

Jersey Mindfulness Project – Risk Assessment

Identified Risks	Likelihood	Potential Impact/Outcome	Risk Management/Mitigating Factors
Practicing mindfulness meditation has been known to trigger distressing memories in patients with existing Trauma/PTSD	Low	Participant: 
 Psychological Stress Researcher 
 Anxiety about dealing with a complex situation 	
 Exclusion criteria for enrolling in the study will include those with pre-existing psychiatric comorbidities, particularly Trauma/PTSD conditions As we are recruiting from primary care GPs will be informed of this criteria as will patients themselves in their information packs The researcher will be able to signpost participant to the relevant support services
Discussion of sensitive topics in interview has	Low	Participant: 
 Psychological Stress 	
 Offer to cease interview Exclusion criteria (as above)

potential to cause distress to participant		
Researcher
 
 Anxiety about dealing with a complex situation 	
 The researcher will be able to signpost participant to the relevant support services
Conflict between participants in group setting	Low	
Participant:
 
 Psychological Stress 
Researcher
 
 Anxiety about dealing with a complex situation 	
 The researcher will have the necessary training and experience in group facilitation to handle conflicts
Data collection & interviews may possibly take place in an unfamiliar location with people not already known to the researcher	High	
Researcher
 
 Physical Injury or Psychological Harm 	
 Visit location prior to data collection to assess possible risks associated with built and social environment Use this information to plan session Identify back up at location or online preferably Allow extra time to familiarise participants with research and environment Researcher to have contact details and means of making timely contact with back up

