
Disclosure of information about poor practice
	
Low
	
Immediate, urgent or prompt response may be required from service providers
	
 • Ensure all verbal and written information about research indicates possible researcher response to disclosure • The researcher will be able to signpost participant to the relevant support services

Disclosure of unmet health or social care needs
	
Medium
	
Immediate, urgent or prompt response may be required from service providers
	
 • Ensure all verbal and written information about research indicates possible researcher response to disclosure • The researcher will be able to signpost participant to the relevant support services

Research participant in danger of harm to self or others
	
Low
	
Immediate, urgent or prompt response may be required from service providers
	
 • Ensure all verbal and written information about research indicates possible researcher response to disclosure • The researcher will be able to signpost participant to the

			relevant support services
--	--	--	------------------------------

Notes to Applicants

1. The Research Ethics Committee requests that all applicants complete the standard application form in a word processed form. Please note, incomplete forms may result in undue delay in considering your proposal. Applications which are not complete or have missing supplementary documentation will not be passed to the Research Ethics Committee and may be returned.
2. The application form is designed to summarise the information concerning your proposed research in order for the Research Ethics Committee to make an assessment. Please ensure that all sections are completed. (See the checklist page 2 of the application form). All relevant supplementary documentation must be included with your completed application form.
3. Please avoid the use of abbreviations and jargon wherever possible and provide a clear explanation of technical terms used for the benefit of lay committee members.
4. The application form is intended to be largely self-explanatory. However, the following comments may assist in completion of this:

Part 1 – Applicant details

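### Adverse effects are emotional only in the monitoring answer but physical or emotional in the ethics section, with no stated record, so physical harms may be missed in the promised report

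*Combined protocol and SAP*

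**What the plan says.** The list of methodological improvements in Part 3, item 2.ii (Rationale) includes "Reporting adverse side effects", with no definition and no limit on type. Four other places bear on what that covers.

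- **Part 4, item 4 (monitoring and handling of problems):** "The lead researcher will be the point of contact for any adverse effects (distressing thoughts or emotions) arising from the intervention". The mitigation that follows is to keep out people with certain psychiatric or substance-use conditions.
- **Part 3, item 3 (Potential to cause distress):** at the start of each group, participants are to be told to speak to the facilitators "should they experience any significant adverse physical or emotional difficulties requiring further medical or psychological attention". The same paragraph says the lead researcher can be reached throughout the project.
- **Part 3, item 3.i:** the form's guidance begins "As well as any physical risks or adverse effects, you should consider the potential for discomfort, distress, inconvenience or change in lifestyle". The applicant's whole answer is a pointer to the risk assessment.
- **Appendix 7 (Risk Assessment Form):** the one risk tied to meditation itself is "Practicing mindfulness meditation has been known to trigger distressing memories in patients with existing Trauma/PTSD", with psychological stress as the impact on the participant. The one entry for bodily injury, "Physical Injury or Psychological Harm", belongs to the researcher.

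The data analysis section (Part 3, item 2.iv) contains no analysis of adverse effects. The available text describes no adverse-effect form, log or tabulation by course.

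**The concern.** These places answer one question differently: does a physical problem count as an adverse effect? Take a participant who tells a facilitator that their pain has become markedly worse during the course and that they need medical attention. Under the ethics section this is exactly what they were asked to raise. It is not among the effects described in the monitoring answer, and Appendix 7 does not foresee it. Nothing tells the facilitator to write it down or pass it on.

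Possible harm is one of the study's own reasons for being done: the scientific abstract raises it, and so does the section on improving on previous research. In people with chronic pain, worsening pain is an obvious harm to look for. A report assembled from emotional events alone would be incomplete on that point, and so would any comparison of adverse-effect counts between the stress and pain courses. Events not noted when they happen are hard to recover later.

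**Working it through.** The plan gives no adverse-effect rate or count, so there is no figure to reproduce. The check is whether the text settles the scope, and then whether other measures fill the gap.

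**1. Scope.** The monitoring answer describes emotional effects only. The ethics section covers physical or emotional difficulties, above a threshold of significance and need for attention. The promise in the Rationale states no scope. None of the three refers to another, so the scope of the report is undetermined. The monitoring answer holds the only gloss on the term, and someone preparing the report could well turn to it.

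**2. Risk table.** Appendix 7 has seven rows.
- Three (distressing memories, sensitive interview topics, conflict in the group) give psychological stress as the participant impact.
- One (unfamiliar locations) gives impacts for the researcher only, and holds the sole mention of physical injury.
- Three (poor practice, unmet needs, and "Research participant in danger of harm to self or others") give a possible service response as the impact.

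3 + 1 + 3 = 7 rows, and none names a physical effect of a course on participants. The form's question about physical risks is therefore unanswered.

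**3. Route.** Participants report to facilitators. The lead researcher is the contact for the emotional effects described in Part 4. No text links the two or requires a record.

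**4. Possible substitutes.**
- *Pain scores.* Outcome measures are taken at baseline, week 1, week 4, within four weeks after the course, and at 3 months; only process measures are weekly. From week 4 of an eight-week course to the post-treatment assessment is about 8 − 4 = 4 weeks at the least and 4 + 4 = 8 weeks at the most. The pain ratings look back no more than a week. So at least about 4 − 1 = 3 of the last four course weeks have no pain rating, and all four have none if the assessment falls more than a week after the course ends.
- *Global impression of change.* This "will allow to consider perceived improvement and deterioration", but it is an overall judgement and does not record what happened or when.
- *Interviews.* These ask about physical worsening, but at most 30 people are interviewed, which is 30/100 = 30% of the planned sample. Anyone with fewer than 6 of 8 sessions is excluded, and that group may include people who stopped because they felt worse.
- *GP and A&E visits.* The comparison is between the waiting period and the time from end of treatment to follow-up. The eight course weeks are in neither window.

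Each captures some worsening. None is a record of adverse effects.

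**The case against.** The strongest reply is that the monitoring answer names a contact person and does not claim to define adverse effects for the study. The sentence after it concerns psychiatric exclusions, so the parenthesis may only describe the risk being mitigated. The promise in the Rationale is unrestricted. All of this stands. A reader might infer that physical harms are shut out of the promised report, and the documents do not support that. They support only that such harms may be left out.

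Second, a reader might infer that the trial could show no difference between the courses in physical effects. That is also too strong. Pain intensity and interference are planned outcomes, to be compared between groups with effect sizes, and the global impression of change includes deterioration. What remains is that these are scores at set times and not counts of events.

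Third, the two reporting routes may be complementary, since the lead researcher is reachable throughout. That is fair, but being reachable is not the same as keeping a record.

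Fourth, it would be wrong to say that Appendix 7 gives participants only psychological impacts. The rows on unmet needs and on danger to self or others concern participants and are of another kind. They deal with disclosure and safeguarding, however, and name no effect of a course.

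Fifth, the floor mats in the budget might be read as a sign of physically demanding courses. Delivery is online, and the mats are listed alongside a group room and refreshments, so nothing about course content follows.

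Last, counting every new or worsened symptom would discard the threshold in the ethics section and could turn ordinary fluctuation in chronic pain into adverse effects. That stands, and the fix respects it.

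**Conclusion.** The inconsistency is real and lies within the operative text: emotional only in the monitoring answer, physical or emotional in the ethics section, and no physical effect of a course on participants in the table offered as the answer on physical risks. With no stated recording or onward reporting, physical adverse effects such as significant pain worsening may be missing from the promised report.

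The size cannot be given. The documents contain no rates, and any percentage of under-counting would only hand back whatever share of events was assumed to be physical.

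The conclusion assumes that no recording procedure exists outside the available text. The participant information and consent pages could not be checked; they may mention physical effects, and their absence is not counted against the plan. The point concerns the completeness of harms reporting and does not touch the planned outcome comparisons. It should be settled before the first course starts.

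**What to change.** - Reconcile Part 4, item 4 and Appendix 7 with the ethics section, so that adverse effects include physical as well as emotional difficulties. State that the report promised in the Rationale uses the same scope. Leave the severity threshold to the investigators, but state it once and apply it to both courses.
- Add a participant row for physical effects of the courses to Appendix 7, so that the form's question on physical risks is answered.
- Have facilitators pass every such report, including those from non-completers, to one log held by the lead researcher, showing date, course and type (physical or emotional).
- Add to the data analysis section a table of counts by course and type.

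The cost is a few changes of wording, one table row and a simple log: slightly more record keeping for facilitators and the lead researcher. Reported counts will be higher than under an emotional-only scope.

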Appendix 7: Risk Assessment Form

Jersey Mindfulness Project – Risk Assessment

Identified Risks	Likelihood	Potential Impact/Outcome	Risk Management/Mitigating Factors
Practicing mindfulness meditation has been known to trigger distressing memories in patients with existing Trauma/PTSD	Low	Participant: 
 Psychological Stress Researcher 
 Anxiety about dealing with a complex situation 	
 Exclusion criteria for enrolling in the study will include those with pre-existing psychiatric comorbidities, particularly Trauma/PTSD conditions As we are recruiting from primary care GPs will be informed of this criteria as will patients themselves in their information packs The researcher will be able to signpost participant to the relevant support services
Discussion of sensitive topics in interview has	Low	Participant: 
 Psychological Stress 	
 Offer to cease interview Exclusion criteria (as above)

potential to cause distress to participant		
Researcher
 
 Anxiety about dealing with a complex situation 	
 The researcher will be able to signpost participant to the relevant support services
Conflict between participants in group setting	Low	
Participant:
 
 Psychological Stress 
Researcher
 
 Anxiety about dealing with a complex situation 	
 The researcher will have the necessary training and experience in group facilitation to handle conflicts
Data collection & interviews may possibly take place in an unfamiliar location with people not already known to the researcher	High	
Researcher
 
 Physical Injury or Psychological Harm 	
 Visit location prior to data collection to assess possible risks associated with built and social environment Use this information to plan session Identify back up at location or online preferably Allow extra time to familiarise participants with research and environment Researcher to have contact details and means of making timely contact with back up


Disclosure of information about poor practice
	
Low
	
Immediate, urgent or prompt response may be required from service providers
	
 • Ensure all verbal and written information about research indicates possible researcher response to disclosure • The researcher will be able to signpost participant to the relevant support services

Disclosure of unmet health or social care needs
	
Medium
	
Immediate, urgent or prompt response may be required from service providers
	
 • Ensure all verbal and written information about research indicates possible researcher response to disclosure • The researcher will be able to signpost participant to the relevant support services

Research participant in danger of harm to self or others
	
Low
	
Immediate, urgent or prompt response may be required from service providers
	
 • Ensure all verbal and written information about research indicates possible researcher response to disclosure • The researcher will be able to signpost participant to the

			relevant support services
--	--	--	------------------------------

Notes to Applicants

1. The Research Ethics Committee requests that all applicants complete the standard application form in a word processed form. Please note, incomplete forms may result in undue delay in considering your proposal. Applications which are not complete or have missing supplementary documentation will not be passed to the Research Ethics Committee and may be returned.
2. The application form is designed to summarise the information concerning your proposed research in order for the Research Ethics Committee to make an assessment. Please ensure that all sections are completed. (See the checklist page 2 of the application form). All relevant supplementary documentation must be included with your completed application form.
3. Please avoid the use of abbreviations and jargon wherever possible and provide a clear explanation of technical terms used for the benefit of lay committee members.
4. The application form is intended to be largely self-explanatory. However, the following comments may assist in completion of this:

Part 1 – Applicant details

Full details should be given of applicant who is proposing to conduct the research project. This must be signed by an academic or clinical supervisor (depending on who is sponsoring and who is supporting the research).

Part 2 – Introduction

Full details should be given of the research team who will be involved in carrying out the research project. If there is only one researcher/investigator he/she will be the Lead Researcher/Principal Investigator for the purposes of the form.

The sponsoring body must be identified. Researchers should carry personal insurance and/or be covered by insurance, or provision made by the employer.

Research sponsored by a pharmaceutical company requires adherence to Association of the British Pharmaceutical Industry Guidelines.

Research undertaken as part of an academic programme of study must have university sponsorship.

Part 3 – The Research

Section 2 Outline of research

It is important that the committee is made aware of the status and type of participant to be recruited and the criteria for inclusion and exclusion of individuals. Please note that in the case of clinical trials, the relative level of acceptable risk may be greater in therapeutic research in patient volunteers (where there is a balancing factor of potential benefit) than in non-therapeutic research using "healthy volunteers".

You must state whether participants will be selected with specific reference to sex, age group and status. You should make clear what proportion of participants recruited (if any) will act as controls.

The effectiveness and propriety of recruitment and selection procedures must be clear. Participants must not be coerced or induced to participate.

Any conflict of interest must be declared, particularly in cases where a participant's relationship with the researcher could raise issues as to the willingness or motive of the participant in consenting to participation (e.g. students).

Section 3 Ethical issues

In discussing the potential risks and hazards which are associated with the research, applicants are required to specify the degree of probability (e.g. percentage terms or as unlikely, possible, likely, expected) and to categorise the risk (e.g. serious, moderate, minor, negligible or in percentage terms). The committee is concerned about the possibility and

nature of anticipated side effects and the nature and extent of the risks that the participant assumes to physical or mental health and well-being by participation.

Section 4 Informed consent

Informed consent is a requirement from all research participants. Where problems may be encountered as a result of language or hearing difficulties, the applicant must explain how these difficulties are to be handled - e.g. interpreter, translation of documents

In any circumstances where the investigator does not anticipate being in a position to obtain participant consent (e.g. studies involving emergency patients, the unconscious, children under 16 who are not judged competent by the investigator to consent in their own right etc.) the applicant must provide full details of the course proposed to be taken with regard to consent and the justification for it. The answer must address the patient's best interests: i.e. will or could enrolment into the research be of therapeutic value to the individual.

Participant information sheets and consent forms must be prepared and presented as separate documents or as an appendix to the application.

In respect of clinical trial research, the participant's GP should be notified before the research commences. Participant consent to such notification (and to further related communication with the GP if necessary) should therefore generally be incorporated into the consent form (and notice of this requirement added to the information sheet). If you do **not** intend to contact participants' GPs, please give reasons.

Section 8 Vulnerable groups

The need to conduct research in "special" or "vulnerable" groups as listed on the application form should be justified. Clarification that the data required could not be obtained from any other class of participant is required. The needs of special groups may indicate extra safeguards/procedures in relation to the provision of information and consent procedures.

Part 4 – Financial and other arrangements

A full statement should be included of all payments, funding and grants which may be made to, or have been agreed with the applicant, his department or employer in connection with the performance of the research. "Payment" includes donations of equipment or other

appliances. (Such financial support should be related to expenses, costs incurred and resources expended in the conduct of the research).

Documents which must accompany the application for ethical opinion of proposed research, where relevant:

- (i) Recruitment advertisement(s) if applicable and any other material proposed to be used for recruitment.
- (ii) GP letter, if applicable
- (iii) Patient information sheet (and letter of invitation, if applicable).
- (iv) Consent form.
- (v) Research protocol (research summary).
- (vi) Where applicable, a copy of regulatory approval in the form of any product licence, Clinical Trial Certificate (CTC), Clinical Trial Exemption (CTX), Doctor's and Dentist's Exemption (DDX) or other authority in writing i.e. proof of regulatory compliance (not applicable in healthy volunteer studies). **Please note that the authority may not extend to Jersey and, in such circumstances, further approval will need to be sought locally.**
- (vii) Data sheet if licensed product(s) are being used in clinical trial research.
- (viii) Administration of Radioactive Substances Advisory Committee (ARSAC) approval, where appropriate.
- (ix) Where applicable, company confirmation of adherence to relevant Association of the British Pharmaceutical Industry (ABPI) Guidelines.
- (x) Risk assessment in compliance with the States of Jersey Health and Social Services, Health and Safety Policy requirements.
- (xi) Full MREC application or university REC application if applicable.
- (xii) Confirmation of favourable opinion from university faculty REC, if applicable. This may be forwarded after the application.
